## **2.5. Sequence of Planned Analyses**

### **2.5.1. Interim Analyses**

No interim analysis is planned for this study.

### **2.5.2. Final Analyses and Reporting**

All final, planned analyses identified in this SAP will be performed only after the last patient has completed the study. The randomization codes will not be unblinded until this SAP has been approved, the database is locked, and the analysis populations are determined.

Any exploratory analyses completed to support study analyses, which were not identified in this SAP, will be documented and reported in appendices to the CSR.

### **3. POPULATIONS /ANALYSIS SETS**

#### **3.1. Intent to Treat (ITT) Population**

The ITT population will include all randomized patients. In this population, treatment will be assigned based upon the treatment to which patients were randomized, regardless of which treatment they actually received.

#### **3.2. Safety Population**

The safety population will include all randomized patients who receive at least 1 dose of study medication. In this population, treatment will be assigned based upon the treatment patients actually receive, regardless of the treatment to which they were randomized.

#### **3.3. Full Analysis Set (FAS)**

The FAS, defined as all patients in the ITT population (all patients randomly assigned to a treatment) who receive at least 1 dose of study drug and have at least 1 post-baseline efficacy assessment, will be used for all efficacy analyses. Summaries will be presented by treatment group. The FAS will serve as the primary analysis set for efficacy analyses.

#### **3.4. Per Protocol Population**

The per protocol analysis set (PP) will include all patients in the FAS who 1) met all inclusion and none of the exclusion criteria, and 2) did not use > 4 days of rescue medication in baseline (days -7 to -1 prior to randomization) and last 7-day window (days 22 to 28) and did not have > 6 pills of rescue medication (1950 mg/day) for any day during that time, and 3) had at least 4 daily average NRS scores for last 7 days of treatment (days 22 to 28) and 4) had at least 70% of study medication compliance between visits 4 and 5.

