- n. Patient has a congenital arrhythmia syndrome (eg, Brugada syndrome or long or short QT syndrome).
- o. Patient has had myocardial infarction within the past 12 months or current unstable angina, coronary ischemia, or heart failure
- p. Patient has significant edema or loss of skin integrity (including sores or ulcers) other than healed herpes zoster skin rash affecting the region of pain and surrounding area.
- q. Patient is intolerant to study drug, its excipients, and/or acetaminophen.
- r. Patient uses any over-the-counter (OTC) analgesic medication/topical therapy for the duration of the study except for permitted rescue (for PHN pain) medications. Stable therapy of more than 30 days for aspirin (up to 81 mg/day) is allowed as cardiovascular prophylaxis.
- s. Patient uses any non-pharmacologic pain management techniques (eg, physical techniques, physiotherapy, massage therapy, acupuncture, biofeedback, and/or psychological support) and is unable or unwilling to discontinue prior to baseline pain assessment.
- t. **[Criterion Removed]**
- u. Patient uses any topical/cosmetic products (eg, lotions and tanning products) on the skin in the painful region of PHN.
- v. Patient has a history of alcohol or drug abuse within 1 year before the screening visit, or a positive urine drug test at the screening visit for cocaine, marijuana, opioids, amphetamines, methamphetamines, benzodiazepines, barbiturates, methadone, and/or tricyclic antidepressants unless explained by the use of prescription medication. (The use of medical marijuana is not permitted and excludes the patient from the study.)
- w. Patient is pregnant or breast-feeding at the time of the screening visit.
- x. Patient has findings in laboratory data, vital signs measurements, or physical examination at the screening, baseline pain assessment interval, or randomization visit that, in the opinion of the investigator, may pose undue risk to the patient or may interfere with study data interpretation.
- y. Patient was previously randomly assigned to treatment in this study and received/subsequently discontinued study drug.
- z. Patient used another investigational drug within 30 days or 5 half-lives (whichever is longer) before the planned first day of study drug application (day 1) in this study.
- aa. Patient refuses to provide 2 blood samples at the screening visit for pharmacogenomic analyses.

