5.3. Prior and Concomitant Therapy or Medication

Any prior or concomitant therapy or medication that a patient has had within 90 days before study drug administration and up to the end of the study period, including follow-up, will be recorded on the CRF. Generic or trade name, indication, and dosage will be recorded. The Sponsor will encode all therapy and medication according to the World Health Organization drug dictionary (WHO Drug).

The following medications will not be allowed during this study:

- Oral analgesics
- Topical analgesics, including lidocaine (gels, creams and patches) and capsaicin patches
- Rescue pain medication except permitted acetaminophen rescue
- Class Ic anti-arrhythmic drugs such as flecainide or propafenone

At each clinic visit after the screening visit, the investigator will ask patients whether they have taken any medications (other than study drug), including OTC medications, vitamins, or herbal or nutritional supplements, since the previous visit. Indication, dosage, and start and end dates should be entered on the CRF.

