7.1.7. Withdrawal Due to an Adverse Event

Any patient who experiences an adverse event may be withdrawn from study drug treatment at any time at the discretion of the investigator. If a patient is withdrawn wholly or in part because of an adverse event, both the adverse events page and the termination page of the CRF will be completed at that time. If possible, a blood sample will be obtained for the measurement of study drug concentrations.

The patient will be monitored at the discretion of the investigator (eg, until the event has resolved or stabilized, until the patient is referred to the care of a health care professional, or until a determination of a cause unrelated to the study drug or study procedure is made). The investigator must inform the CPP/CL as soon as possible of all patients who are being considered for withdrawal due to adverse events. Additional reports must be provided when requested.

If a patient is withdrawn from study drug treatment and/or the study for multiple reasons that include adverse events, the termination page of the CRF should indicate that the withdrawal was related to an adverse event. An exception to this requirement will be the occurrence of an adverse event that, in the opinion of the investigator, is not severe enough to warrant

discontinuation but that requires the use of a prohibited medication, thereby requiring discontinuation of the patient. In such a case, the reason for discontinuation would be need to take a prohibited medication, not the adverse event.

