9.3.4. Per Protocol Population

The PP population will include all subjects in the FAS who have not had major protocol deviations (ie, protocol violations). Protocol violations will be determined before unblinding. The PP Population will serve as the supportive population for efficacy analyses.

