11.1.2. Protocol Deviations

A protocol deviation is any change, divergence, or departure from the study design or procedures defined in the protocol.

Important protocol deviations, referred to as protocol violations, are a subset of protocol deviations that may significantly impact the completeness, accuracy, and/or reliability of the study data or that may significantly affect a patient's rights, safety, or well-being. Protocol violations include enrolling patients in violation of key eligibility criteria designed to ensure a specific subject population; failing to collect data necessary to interpret primary endpoints; noncompliance to study drug administration; use of prohibited medications; or any other deviations that may have an impact on the processes put in place for the care and safety of the patients or compromise the scientific value of the trial. Protocol violations will be identified and recorded by study site personnel on the CRF. All protocol violations will be reported to the responsible IEC/IRB, as required.

When a protocol violation is reported, the Sponsor will determine whether to discontinue the patient from the study or permit the patient to continue in the study, with documented approval from the medical representative. The decision will be based on ensuring the safety of the patient and preserving the integrity of the study.

Deviations from the inclusion/exclusion criteria of the protocol are **not** prospectively granted by the Sponsor. If study site personnel learn that a patient who did not meet protocol eligibility criteria was entered into a study, they must immediately inform the Sponsor of the protocol violation. If such patient has already completed the study or has withdrawn early, no action will be taken but the violation will be recorded. If such patient is still participating in the study, a determination will be made by the sponsor and the investigator as to whether it is in the best interest of the patient to continue in the study.

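### The SAP's per-protocol definition does not remove patients who start a prescribed oral analgesic after randomization, although the protocol's definition does

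*SAP*

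**What the plan says.** Protocol 9.3.4: "The PP population will include all subjects in the FAS who have not had major protocol deviations (ie, protocol violations". Violations are to be settled before unblinding. Protocol 11.1.2 lists among them "noncompliance to study drug administration; use of prohibited medications". Protocol 5.3, under "The following medications will not be allowed during this study", names oral analgesics, topical analgesics and any rescue other than the permitted acetaminophen.

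SAP 3.4 defines the set differently: "The per protocol analysis set (PP) will include all patients in the FAS who 1) met all inclusion and none of the exclusion criteria". Three further conditions follow:
- Condition 2: rescue medication on no more than 4 days in the windows -7 to -1 and 22 to 28, and the patient "did not have > 6 pills of rescue medication (1950 mg/day) for any day during that time".
- Condition 3: four or more daily average scores in days 22 to 28.
- Condition 4: study drug compliance of 70% or more between visits 4 and 5.

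No condition mentions prohibited medication or protocol violations. SAP 5.7 tabulates violations without tying them to PP membership. The SAP Preface gives the SAP precedence over the protocol. SAP section 10 lists three changes to the protocol's analyses, and the PP definition is not among them.

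**The concern.** A PP set is meant to show whether the result holds among patients who followed the protocol. An analgesic taken in the endpoint week acts directly on the outcome, so it is among the violations such a set should remove. The protocol's rule removes it. The SAP's rule can leave it in, and the SAP is the rule that will be programmed.

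The PP set is used for the primary variable (table 15.2.1.2) and the responder rates (15.2.5.2), among others. The responder table is likely to be read closely. According to Protocol 3.2, the previous crossover trial in postherpetic neuralgia missed its primary endpoint, and its 50% responder signal came from the efficacy-evaluable and PP groups. The two sensitivity analyses in SAP 6.2.3 deal with dropout and excessive rescue use, not prohibited analgesics. In the unredacted text, the PP set is therefore the only planned analysis that could address them.

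**Working it through.** **Testing the conditions.** Take a patient who was eligible at entry and is prescribed an oral opioid after day 1.

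1. *Eligibility.* Exclusion d concerns therapy already in use and an unwillingness or inability to wash it out. Exclusion r is the analgesic criterion worded to run through the study, but it is written for non-prescription products: "Patient uses any over-the-counter (OTC) analgesic medication/topical therapy for the duration of the study except for permitted rescue". Inclusion g asks for willingness to comply and is judged at entry. None clearly reaches this patient.
2. *Rescue limits.* If rescue means the supplied acetaminophen, as the pill count and 1950 mg cap suggest, opioid use of any length passes. If it means any drug taken for pain rescue, use on up to 4 of the 7 endpoint days still passes.
3. *Diary scores.* Scores on days 22, 23, 24 and 25 are enough. The condition removes the patient only if fewer than four daily averages exist, for example when the diary stops before day 25.
4. *Compliance.* This measures ointment use only.

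The patient meets all four conditions and fails the protocol's rule.

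**Size.** The inputs are the SD of 2.35, 88 per arm and the 1.0 to 1.3 point range for gabapentin and pregabalin (Protocol 9.2, SAP 2.3). The planned sample size reproduces: a two-sample t-test at two-sided 5% with 80% power for a 1.0-point difference needs 87.66, rounded up to 88 per arm. Allowing for 20% dropout, 88 / 0.80 = 110.

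Planned standard error of a difference: 2.35 × √(2/88) = 0.354.

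The shift in the PP mean difference is the imbalance in use between arms times the benefit per user. Both are assumptions, because the documents give no usage rate. The 1.0 to 1.3 range is a stand-in for the benefit.

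| Imbalance | Benefit 1.0 | Benefit 1.3 |
|---|---|---|
| 0 | 0 | 0 |
| 5 points | 0.050 | 0.065 |
| 10 points | 0.100 | 0.130 |

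In standard errors the range is 0.05/0.354 = 0.14 to 0.13/0.354 = 0.37. If condition 2 covers all pain rescue and benefit is confined to days of use, multiply by 4/7: 0.029 to 0.074 points, or 0.08 to 0.21 standard errors.

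The direction depends on which arm has more users. With more on placebo and a true difference of 1.0, the PP estimate falls to between 0.95 and 0.87. With more on active treatment it rises to between 1.05 and 1.13.

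**Cost of removing such patients.** If 5% to 10% of each arm left the PP set, 88 becomes about 84 to 79. The standard error becomes 2.35 × √(2/84) = 0.363 (up 2.4%) to 2.35 × √(2/79) = 0.374 (up 5.5%).

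**The case against.** **Such patients may leave anyway.** Protocol 7.1.7 describes an adverse event that "requires the use of a prohibited medication, thereby requiring discontinuation of the patient", and a patient who stops the diary before four week 4 scores exist fails condition 3. Protocol 7.3.4.2 bars continued participation after a positive urine screen that has no medical explanation. These routes will remove some users but do not close the gap. Section 7.1.7 covers the adverse-event case, a prescription may count as a medical explanation, and under 11.1.2 "the Sponsor will determine whether to discontinue the patient from the study or permit the patient to continue in the study".

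**Fixed conditions are a defensible choice.** Objective criteria avoid case-by-case rulings on violations. That supports writing conditions down. It does not explain why prohibited analgesics were left out, and the SAP gives no reason.

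**Removal has its own bias.** Starting an analgesic may reflect treatment failure, so excluding such patients selects on a post-randomization event. This is true, but it applies to any PP set and to the protocol's own rule. It should be stated as a limitation.

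**The size is assumed.** This stands. A 10-point imbalance requires about 9 of 88 patients (0.10 × 88 = 8.8) in one arm to use such a drug and still meet every condition. The benefit range comes from whole-arm differences in other trials and may be too large for someone who starts in week 4.

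**Stronger readings that the documents do not support.**
- A reader might infer that any prohibited analgesic passes. Exclusion r arguably catches non-prescription analgesics, and its reference to topical therapy may catch prescribed topical products. The clear gap is prescribed oral analgesics.
- A reader might infer that the eDiary already records this use. Footnote ee of Protocol Table 1 concerns rescue taken in periods when rescue is not allowed. Other drugs are captured by the medication inquiry at visits (Protocol 5.3).
- A reader might treat the silence in SAP section 10 as a breach. The SAP Preface and Protocol 9.13 allow the difference to be explained in the study report, so it is secondary.

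**Conclusion.** The discrepancy is real. Following SAP 3.4 as written can keep in the PP set a patient whom Protocol 9.3.4 removes, and nothing else in either document reliably prevents it. This rests on the text and not on any assumed rate.

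The consequence is limited. A reader might infer that the main efficacy result is at risk, but the primary analysis uses the full analysis set and is unaffected. A reader might also infer that the PP results will be biased. The documents do not show this: usage is unknown, and the bias in the mean difference is zero if use and benefit are equal across arms. Under the assumptions above, the shift is 0.05 to 0.13 NRS points in either direction, or 0.03 to 0.07 if condition 2 is read to cover all pain rescue. No effect on the responder table has been calculated. Severity is low.

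**What to change.** Add a fifth condition to SAP 3.4: *and took no prohibited analgesic (Protocol 5.3 or Appendix A Table 2), other than the supplied acetaminophen rescue governed by condition 2, on days -7 to -1 or 22 to 28, as identified before unblinding from the concomitant medication records and the visit 5 urine drug screen*.

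The acetaminophen exception is needed. Protocol 5.4 does not permit rescue in the baseline interval or the final week, so without the exception one tablet in week 4 could remove a patient whom condition 2 tolerates. Appendix A is named because it lists the anticonvulsants and antidepressants to be washed out, which 5.3 does not name. List the changed PP definition in SAP section 10.

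The cost is one condition and one line, made before the analysis populations are fixed under SAP 2.5.2. It needs no new data and no protocol amendment. The PP set becomes slightly smaller, with a standard error about 2% to 6% larger if 5% to 10% of each arm are removed. It also carries the post-randomization selection common to any PP set.

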5.5. Procedures for Monitoring Patient Compliance

Each investigator or designee will be responsible for monitoring patient compliance. Study drug exposure will be measured, and compliance to study drug administration will be monitored by weighing the tubes of blinded study drug at the week 2 (visit 4, day 15 ±1) and week 4 (visit 5, day 29) or ET visits. (At visit 3, the tubes will be weighed to obtain a baseline weight.) A patient will be considered compliant during the interval between the previous 2 visits if the tube weighs between 70% and 120% of the expected weight. Also, study drug accountability records will be completed. Patients will not be discontinued for noncompliance at week 2 (visit 4, day 15 ±1); however, they will be retrained in proper medication dispensing.

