## PREFACE

This Statistical Analysis Plan (SAP) describes the planned analysis and reporting for TEVA Branded Pharmaceuticals Products R&D, Inc. study TV-45070-CNS-20013, (A Phase 2, Randomized, Double-Blind, Placebo-Controlled Study to Evaluate the Safety and Efficacy of Topically Applied TV-45070 (4% and 8% w/w Ointment) in Patients with Postherpetic Neuralgia), and was written in accordance with SOP GBP\_RD\_702.

This phase 2 study is being completed to assess the safety and efficacy of topically applied TV-45070 (4% and 8% w/w Ointment) in patients with postherpetic neuralgia.

The structure and content of this SAP provides sufficient detail to meet the requirements identified by the FDA and International Conference on Harmonization of Technical Requirements for Registration of Pharmaceuticals for Human Use (ICH): E9 Guidance on Statistical Principles in Clinical Trials. All work planned and reported for this SAP will follow internationally accepted guidelines, published by the American Statistical Association, and the Royal Statistical Society, for statistical practice.

The following documents were reviewed in preparation of this SAP:

- Clinical Study Protocol TV-45070-CNS-20013, issued 20 November 2014.
- Case report forms (CRFs) for Study TV-45070-CNS-20013, issued 19 December 2014.
- ICH E9 Guidance on Statistical Principles for Clinical Trials.
- ICH E3 Structure and Content of Clinical Study Reports.

The reader of this SAP is encouraged to also read the clinical protocol for details on the conduct of this study, and the operational aspects of clinical assessments and timing for completing a patient in this study. When differences exist in descriptions or explanations provided in the protocol and this SAP, the SAP prevails; the discrepancies will be explained in the CSR.

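### SAP 3.4 narrows the protocol's per-protocol definition without declaring it: a prescription oral analgesic taken after randomisation, or drug use above 120% of expected, no longer removes a patient

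*SAP*

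**What the plan says.** Protocol 9.3.4 gives a general rule: "The PP population will include all subjects in the FAS who have not had major protocol deviations (ie, protocol violations"), with violations determined before unblinding. Protocol 11.1.2 says what counts, and its list includes "noncompliance to study drug administration; use of prohibited medications". Two other protocol sections give those terms content. Section 5.3 opens its list with "The following medications will not be allowed during this study" and names oral analgesics first. Section 5.5 calls a patient compliant over a visit interval "if the tube weighs between 70% and 120% of the expected weight".

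SAP 3.4 does not refer to violations. It keeps FAS patients who meet four conditions:

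1. they "met all inclusion and none of the exclusion criteria";
2. they stay within limits on rescue use, beginning "did not use > 4 days of rescue medication in baseline (days -7 to -1 prior to randomization") and applying also to days 22 to 28;
3. they have at least 4 daily average pain scores in days 22 to 28;
4. they "had at least 70% of study medication compliance between visits 4 and 5".

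The SAP Preface settles conflicts: "When differences exist in descriptions or explanations provided in the protocol and this SAP, the SAP prevails". It adds that discrepancies will be explained in the clinical study report. SAP Section 10, which lists changes to protocol-specified analyses, has three entries (demographic comparisons, weeks in the primary model, time to response). The PP definition is not among them.

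**The concern.** A PP analysis is meant to show the effect in patients treated as planned. In an analgesic trial the most damaging departure is another analgesic taken while the endpoint is being recorded. It lowers the week 4 score, and the analysis credits the relief to the assigned arm. If it is commoner on placebo it hides a true effect; if commoner on active drug it exaggerates one.

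No other planned analysis of the primary endpoint deals with this. Both sensitivity analyses in SAP 6.2.3 act on the reason for discontinuation and on excessive rescue use, not on prohibited analgesics. The PP set was the place for the check.

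The set also carries some weight in this programme. SAP 12.1 tabulates it for the primary endpoint, evening pain, responder rates, PGIC and DSIS. Protocol 1.1 and 3.2 say that the earlier crossover trial in PHN missed its primary endpoint and that its positive responder finding came from the efficacy-evaluable and PP groups.

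**Working it through.** **Step 1: prohibited analgesic.** Take a patient who completed washout, was eligible at randomisation, starts a prescription oral opioid in week 3, takes no acetaminophen, fills in the diary and applies 100% of the expected ointment.

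- Criterion 1 (eligibility): exclusion d asks whether the patient is unwilling or unable to wash out, and this patient did wash out. Exclusion r runs through the study but is worded for over-the-counter analgesics and topical therapy. Inclusion g concerns willingness to comply at entry. Passed.
- Criterion 2 (rescue): its limit of 6 pills or 1950 mg per day is that of the supplied acetaminophen. Passed.
- Criterion 3 (diary): passed.
- Criterion 4 (at least 70%): passed.

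Under SAP 3.4 the patient is in the PP set. Under Protocol 9.3.4 with 11.1.2 and 5.3, the patient has a violation and is out.

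**Step 2: compliance.** SAP 7.2 defines compliance = 100 × amount used / amount expected, and already tabulates a category above 120%. Applying each rule to test values:

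| Compliance | SAP 3.4 (≥ 70%) | Protocol 5.5 range (70% to 120%) |
|---|---|---|
| 60% | out | noncompliant |
| 70%, 100%, 120% | in | compliant |
| 121%, 150%, 200% | in | noncompliant |

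The rules differ only above 120%, where SAP 3.4 keeps everyone.

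**Step 3: size, as illustration only.** First the plan's own figure (Protocol 9.2, SAP 2.3: difference 1.0, SD 2.35, two-sided 5%, 80% power). The normal formula 2 × (1.960 + 0.842)² × 2.35² / 1.0² gives 86.7, so 87 per arm. The t-test version gives 87.66, so 88, with 80.2% power. Then 88 / 0.80 = 110. The plan's figures reproduce.

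Let f be the excess share of placebo PP patients on a prohibited analgesic, compared with the active arm, and e their extra relief in points. The observed difference is d = 1.0 − f × e. With 88 per arm the standard error is 2.35 × √(2/88) = 0.354, and power ≈ Φ(d / 0.354 − 1.96), which is 80.6% at d = 1.0. For e I take 1.0 to 1.3, the range of active-placebo differences that Protocol 9.2 cites for gabapentin and pregabalin. For f I assume 5% to 20%; the documents give no figure.

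| f | e | d | Power at 88 per arm |
|---|---|---|---|
| 5% | 1.0 | 0.95 | 76.5% |
| 5% | 1.3 | 0.935 | 75.2% |
| 10% | 1.0 | 0.90 | 71.9% |
| 10% | 1.3 | 0.87 | 69.0% |
| 20% | 1.0 | 0.80 | 61.7% |
| 20% | 1.3 | 0.74 | 55.1% |

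Equal use in both arms would give f = 0 and no shift. The trial was not powered on the PP set, so the last column is only a scale.

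**The case against.** The case against has several parts, and much of it limits the point.

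*Such a patient may leave the set anyway.* Protocol 7.1.7, in the setting of an adverse event, treats need for a prohibited medication as a reason for discontinuation, and a patient stopped in week 3 would ordinarily fail criterion 3 for lack of scores. But Protocol 11.1.2 lets the Sponsor keep a patient with a violation in the study, so removal is not assured. The visit 5 urine screen covers opiates, but it comes after the last dose, Protocol 7.3.4.2 acts only on positives without a medical explanation, and no PP criterion uses the result.

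*A topical lidocaine user is already removed.* A reader might infer that this patient stays in too. The documents do not clearly support that: exclusion r arguably reaches topical therapy during the study and enters through criterion 1. The gap is clear only for prescription oral analgesics.

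*The protocol never names over-application.* This is correct. Section 5.5 speaks of tube weight, and read literally a heavy tube means too little was used. The over-use reading rests on SAP 7.2, which works with amount used. No document shows harm from it, so this part is a mismatch of limits and nothing more.

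*Looking only at visits 4 to 5 is defensible.* A reader might infer that ignoring earlier compliance is a fault. Week 4 is the endpoint, and Protocol 5.5 retrains week 2 noncompliers instead of discontinuing them. I do not press this.

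*The stakes are low.* PP is supportive, populations are fixed before unblinding (SAP 2.5.2), and major violations and use above 120% are tabulated (SAP 5.7, 7.2). All true. But the tables show how many patients are affected, not what the PP estimate would be without them.

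**Conclusion.** The conflict stands. For two of the violations that the protocol names, SAP 3.4 is looser than Protocol 9.3.4: it keeps a patient on a prescription oral analgesic after randomisation, and it drops the upper compliance limit. The looser text governs, and Section 10 is silent. The Preface's promise of an explanation in the study report comes after the data are known and does not replace a declared change.

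The effect is confined to the supportive analysis; the FAS analysis and the sample size do not change. Its size and direction are unknown. The range of 0.95 to 0.74 depends wholly on the assumed f and e and on the excess being on placebo. A reader might infer that the PP set cannot show a treatment effect, or that the bias has a known size; neither follows. With a standard error of about 0.35, a shift of 0.1 points would be about 0.3 standard errors. What follows is that the set does not do the check for which the protocol defined it.

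**What to change.** Before unblinding, amend SAP 3.4 as follows.

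- Add: '5) had no major protocol violation as defined in protocol 11.1.2, including use of a prohibited medication during the treatment period through day 28, determined before unblinding (acetaminophen rescue remains governed by criterion 2, study drug compliance by criterion 4, and aspirin permitted under exclusion r is not a violation)'.
- Change criterion 4 to: '70% to 120% compliance between visits 4 and 5, computed as in SAP 7.2'.
- List in SAP Section 10 any departure from Protocol 9.3.4 that remains. Two would: rescue use is judged by criterion 2's limits, and compliance is judged in one interval only. If the sponsor prefers to keep the present criteria, that choice belongs in Section 10 with its reason.

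The carve-outs matter. A bare ban on everything in Protocol 5.3 would remove patients for acetaminophen use that criterion 2 tolerates and would catch the permitted low-dose aspirin. A ban limited to the baseline and final weeks would miss use confined to week 3.

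The cost is SAP wording and a slightly smaller supportive set. No new data are needed: concomitant medication with dates is on the CRF (Protocol 5.3), SAP 5.7 already summarises major violations, and SAP 7.2 already derives the compliance ratio. As with any PP set, selection on behaviour after randomisation remains, so FAS should stay primary.
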